#### 20.3.2. Individuals

At the individual level, the primary quantitative marker of process will be change in shopping habits as measured by number of weekly visits to the study store around which individuals are clustered, and total weekly spend and proportion of weekly food spend spent at the study store. This will be assessed using a shopping habits questionnaire at baseline and follow up.

#### 21. SAMPLING & RECRUITMENT

The sampling and recruitment procedures will vary across the three components of the research. The National Centre for Social Research (NatCen) will be responsible for recruitment of individual cluster RCT participants.

#### 21.1. Cluster RCT

The cluster RCT will involve recruiting stores as well as individual participants who are regular users of those stores, and assessment and follow up of individual participants.

# 21.1.1. Sampling of stores

A sampling frame of all stores meeting the inclusion criteria, except the distance criterion (see section 11.1.1), will be supplied by relevant individuals at DH & ACS. All stores in the sampling frame will be stratified according to Government Office Region, socio-economic deprivation and store size. The exact nature of the deprivation and size strata will be determined once data on these stratifying variables have been examined. Pairs of stores (which are more than 1km from each other or other pairs) will then be randomly selected from each stratum for inclusion in the research. If stores are selected that are within 1km of previously selected stores, re-sampling will take place. Within each pair one store will be randomised to the intervention arm of the study and one to the control arm.

#### 21.1.2. Recruitment of stores

Stores selected to take part in the research will be informed in a letter and information sheet sent to store managers and during a follow-up telephone call and visit to stores from a researcher. During this visit the research process will be described and full informed consent to take part in the research will be obtained

from managers. Any stores that refuse to participate will be replaced by resampling until the required sample size is achieved. Stores will be informed of the trial arm to which they have been randomised in a letter following baseline data collection.

# 21.1.3. Sampling of individual participants

The target population will be all those who meet the inclusion criteria (see section 12.1.2). However, as it will not be possible to compile a complete sampling frame, we will use systematic-, rather than simple-, random sampling to select individuals to be invited to participate. The distribution of adult visitors by day and time to each study store ('footfall') will be estimated using baseline EPOS data. Days will be split into five three hour shifts from 7am-10pm across the seven days of the week and individuals will then be selected, proportional to footfall, from a sample of 12 shifts per store balanced across days and times within and between stores. This should ensure that those invited to take part are reasonably representative of all store users, in terms of day and time of store use.

# 21.1.4. Recruitment of individual participants

Based on previous research, we estimate that around 40% of individuals invited to take part in the study will agree. Potential participants will be recruited in-store by trained NatCen fieldworkers who will approach adult shoppers and invite them to take part in a short screening questionnaire to confirm the inclusion criteria. If these are met, the research will be explained and individuals will be invited to take part. Those who express interest will be given a written information sheet and asked to provide contact details so a home visit from a trained NatCen fieldworker can be arranged.

#### 21.2. Economic evaluation

The individual and store level data used in the economic evaluation will be collected as part of the cluster RCT and process evaluation. Sampling and recruitment will, therefore, be as per those components.

#### 21.3. Process evaluation

The qualitative element of the process evaluation will involve recruiting stores as well as individual participants who are regular users of those stores, alongside retail sector personnel working at those stores, and intervention implementation professionals.

#### *21.3.1. Sampling of stores*

A sub-sample of study stores taking part in the cluster RCT will be purposively sampled to reflect the same sampling strata used to select stores for the cluster RCT and to include most of the symbol groups participating in the intervention. Customers and retail sector personnel participants in the qualitative element of the process evaluation will be selected from around these study stores.

#### 21.3.2. Sampling and recruitment of customers

Regular users of selected study stores will be recruited using the same techniques as described for the cluster RCT, although recruitment will be by trained researchers from Stirling University, not NatCen. That is, a trained researcher will approach adult shoppers and invite them to take part in a short screening questionnaire to confirm the inclusion criteria. If these are met, the research will be explained and individuals will be invited to take part. Those who express interest will be given a written information sheet and asked to provide contact details so telephone calls can be made to arrange focus group sessions.

Individuals will then be purposively sampled to reflect the socio-demographic profile of individuals participants in the cluster RCT from amongst those who express interest in taking part in the research. These individuals will be telephoned and invited to attend focus groups at convenient community locations.

21.3.3. Selection and recruitment of retail sector personnel and intervention implementation professionals Retail sector personnel will be purposively sampled to reflect store owners, store managers, Fresh Food Champions, and other members of staff. Key people involved in the implementation of the intervention will be purposively sampled and include members of the DH implementation team, key decision makers from symbol groups taking part in the intervention, and symbol group regional managers. Potential participants will be invited to take part in interviews via a telephone call to their place of work introducing the research and explaining the research process. Interviews will take place at participants' place of work, or other convenient locations.

#### 22. RANDOMISATION

Randomisation will take place only at the store level within the cluster RCT. We will employ simple randomisation within pairs of stores (the digital equivalent of tossing a fair coin) to allocate one of the two stores to the intervention. Randomisation will be performed by the trial statistician at Newcastle University.

#### 23. ASSESSMENT AND FOLLOW-UP

#### 23.1. Cluster RCT

# 23.1.1. Baseline assessment of individuals

Individual participants will be contacted by telephone soon after in-store recruitment to arrange a home visit from a trained NatCen fieldworker. During these telephone calls, participants will be asked whether they would prefer reminders the day before home visits are due to take place to be made via telephone or SMS text message, and to provide an appropriate telephone number to facilitate this. Participants will be telephoned, or sent SMS text messages, as appropriate, the day before home visits are due to take place as a reminder and to confirm arrangements.

During home visits, participants will be given a further verbal explanation of the research process and the opportunity to ask any questions they have of the researcher. They will then be invited to confirm their willingness to proceed by completing a written consent form. Next, a socio-demographic questionnaire will be completed and the process of the two-day food diary explained. Finally, the researcher will explain that a questionnaire collecting information on household grocery shopping habits will be completed at the follow-up visit when the food diary is collected and that participants may want to discuss the issues that this questionnaire will cover with the main household grocery shopper (if this is someone other than the respondent) in the interim. A card describing the main topics in the shopping habits questionnaire will be left with participants.

Participants will be provided with a food diary in which to record all food and drink consumed with time of consumption and approximate weights over two consecutive days, with the first day of recording chosen using a quota method to ensure approximately equal numbers of individuals per store begin recording on the same day of the week. When placing the diary, interviewers will use a protocol to explain it to the respondent, going through the different sections including the instruction page, information on describing details of food and drink and portion sizes and an example day. The diary will provide photographs of frequently consumed foods as small, medium and large portion sizes which respondents can use for identical or similar foods. Otherwise portion sizes will be in household measures or, for packaged foods, the weight indicated on the packet. Respondents will also be asked to collect the food label information/wrappers for any unusual foods and ready meals consumed to help coders identify or clarify items consumed.

Food diaries will be collected at a second visit no later than three days after the last diary day. Interviewers will review the diary with the respondent to identify and edit possible omissions and missing detail. The shopping habits questionnaire will then be administered. At this visit, participants will also be given a form and return envelope to inform the study team of changes of address or change of circumstance (including where a study participant has died) between baseline and follow up. All participants who complete a food diary will be given a £20 shopping voucher as a 'thank you' gesture. As soon as possible after this follow-up visit, fieldworkers will complete an evaluation of food diaries indicating their assessment of the quality of data collected.

In any cases where participants are not at home when a fieldworker arrives for a home visit, efforts will be made to re-arrange by telephone on a maximum of five occasions on different days of the week and at different times of day. This will occur after a maximum of two broken appointments.

#### 23.1.2. Follow up assessment of individuals

All individuals who complete baseline assessments will be sent a 'thank you' letter around six months after baseline that also reminds them of follow up assessments at 12 months. A further change of address and change of circumstance form and return envelope will be included with this letter. Twelve months after baseline participants will be re-contacted, via letter and then telephone, to arrange another home visit from a trained NatCen fieldworker and the preferred method of sending confirmation details determined. The

procedure for data collection will be largely as at baseline, although written informed consent will not be collected again. Additional questions concerning awareness of the intervention will be included in the shopping habits questionnaire at follow up. Each participant will complete a food diary for the same two days of the week at follow up as they did at baseline.

Following complete of final data collection at follow-up, all participants will be given a further £20 shopping voucher as a "thank you" gesture.

In any cases where participants are not at home when a researcher arrives for a home visit, efforts will be made to re-arrange by telephone on a maximum of five occasions on different days of the week and at different times of day. This will occur after a maximum of two broken appointments.

Whenever data is collected the researchers will adhere to good practice in maintaining confidentiality of information given and data will be anonymised as soon as practicable. The Newcastle University Institute of Health and Society, Code of conduct on confidentiality (in appendix A) will be used to guide appropriate procedures.

#### 23.2. Economic evaluation

The majority of the data used in the economic evaluation will be collected as part of the cluster RCT and process evaluation components and assessment will, therefore, be as per those components. The topic guide for the qualitative element will incorporate topics relevant to the economic evaluation such as time taken up by the initiative and impact on staff. In addition, costs of the intervention associated with DH and individual c-stores will be assessed, including any labour, consumables and any other costs. Where necessary this additional data will be accessed by telephone calls to the store managers and regional managers. Data from the cluster RCT and process evaluation (e.g. food diary data and shopping habits questionnaire, in store observation and contemporary web data) will be used to estimate costs to consumers associated with changing consumption patterns.

#### 23.3. Process evaluation

#### 23.3.1. Quantitative element

Collection of shopping habits data is detailed in sections 23.1.1 and 23.1.2. The other aspects of the quantitative process evaluation are analyses of EPOS data and in-store observations. Information on sales of FFV over one week at baseline, one month and 12 month follow up will be provided by store managers from their EPOS records.

Information on available FFV will be assessed by direct observation by researchers visiting individual stores. An in-store observation instrument will be used to collect data at baseline; one and 12 month follow up to assess variety, cost and quality of FFV and to assess how the intervention has been implemented in intervention stores at one and 12 month follow up. With store managers' permission, we will also take digital photographs of the inside and outside of study stores to keep a permanent record of use of C4L branded materials and FFV displays. Cost comparison data will be accessed via web based searches of a major high street retailer's on-line store for the costs of a comparable range of FFV to that currently available in the study c-store within eight days of each individual c-store visit.

Although researchers will make themselves known to managers on arrival for observations and seek permission to conduct observations, these visits will be unannounced.

# 23.3.2. Qualitative element – focus groups with customers

Arrangements for attendance at focus groups made during recruitment telephone calls will be confirmed in a letter sent with a further copy of the information sheet. During recruitment telephone calls, participants will be asked whether they would prefer reminders the day before focus groups are due to take place to be made via telephone or SMS text message, and to provide an appropriate telephone number to facilitate this. Participants will be telephoned, or sent SMS text messages, as appropriate, the day before focus groups are due to take place as a reminder and to confirm arrangements.

Consumers will be welcomed to focus groups with light refreshments and a brief verbal description of the research process and discussion of the ground rules for focus groups. Participants will then be invited to ask

any questions they have of the researchers and to complete a written consent form. Following focus groups, participants will be thanked for their input and given £20 shopping voucher as a "thank you" gesture.

Focus group discussions will be guided by a topic guide developed during pilot work, and with participants' consent, will be audio recorded. Recordings will be transcribed verbatim for analysis.

No attempts will be made to recontact participants who do not attend focus groups as arranged.

# 23.3.3. Qualitative element – one-to-one interviews with retail sector personnel and intervention implementation professionals

Arrangements for one-to-one interviews made during recruitment telephone calls will be confirmed in a letter sent with a copy of the information sheet. During recruitment telephone calls, participants will be asked whether they would prefer reminders the day before interviews are due to take place to be made via telephone or SMS text message, and to provide an appropriate telephone number to facilitate this. Participants will be telephoned, or sent SMS text messages, as appropriate, the day before interviews are due to take place as a reminder and to confirm arrangements.

Interviews will begin with a brief verbal description of the research process. Participants will then be invited to ask any questions they have of the researcher and to complete a written consent form. Following interviews, participants will be thanked for their input and given £20 shopping voucher as a "thank you" gesture.

Interviews will be guided by a topic guide developed during pilot work, and with participants' consent, will be audio recorded. Recordings will be transcribed verbatim for analysis.

In any cases where participants are not available when a researcher arrives for a one-to-one interview, efforts will be made to re-arrange by telephone on a maximum of five occasions on different days of the week and at different times of day. This will occur after a maximum of two broken appointments. If arranging a face-to-face interview proves impossible, telephone interviews will be conducted.

#### 24. BLINDING

Blinding will only be of importance in the cluster RCT – participants in the qualitative element of the process evaluation will be actively encouraged to discuss the intervention. At baseline, we will not inform fieldworkers or individual cluster RCT participants what the intervention being studied is, nor whether stores have been allocated to the intervention or control group. By 12 month follow up it is possible that both individual cluster RCT participants and fieldworkers will have noticed local C4L branded c-stores. However, again we will not specifically tell either participants or fieldworkers what the intervention being studied is. There will be some questions concerning awareness of the intervention at follow up so. For these reasons, we will not be able to prevent awareness of the intervention or group allocation by 12 month follow up in all cases and the cluster RCT technically falls within the definition of an 'unblinded' RCT.

# 24.1. Cluster RCT

#### 24.1.1. Stores

It will be impossible to blind store staff to the group they have been allocated to, and no attempt will be made to do this. Store managers will be informed whether they have been allocated to the control or intervention group after baseline data collection via a letter.

#### 24.1.2. Individuals

Individuals will not be informed of the specific intervention that the study is evaluating or the specific outcome of interest. However, if they regularly use an intervention group study store it is unlikely that they will not notice changes made as a result of the intervention. Participants will be asked at follow up if they are aware of the intervention in general, or in a store they regularly shop at.

#### 24.1.3. Research staff

NatCen fieldworkers will not be informed of the specific intervention that the study is evaluating, the specific outcome of interest, or the study group that stores have been allocated to at baseline. However, it is possible that they will become aware of the intervention being studied and the study group that stores have

been allocated to at follow up during travels in the local area and during administration of questions on awareness of the intervention. No steps will be taken to avoid this.

#### 25. RETENTION AND MINIMISATION OF LOSS TO FOLLOW UP

As the primary outcome of interest is the effect of the intervention at the individual, rather than store, level, we will be most concerned with loss to follow up of individual cluster RCT participants, but drop out of stores is also possible. Loss to follow up will not be a concern in the qualitative element as participants will not be followed up.

#### 25.1. Cluster RCT

#### 25.1.1. Stores

We will not make any specific attempts to minimise loss to follow up amongst study stores. If any stores do drop out from intervention implementation, we will identify this during 12 month in-store observations.

#### 25.1.2. Individuals

We will take a number of steps to minimise loss to follow up, including:

- Ensuring participants understand the full research process when they agree to take part at baseline
- · Arranging all home visits at a time convenient to participants
- Reminding participants of home visits the day before they are due to take place by telephone or SMS text message – as preferred by the participant
- Offering financial incentives to all individuals who complete the research
- Making substantial efforts to rearrange any missed home visits
- Leaving change of address notification forms with participants at the end of baseline data collection
- Sending updates to participants around 6 months after baseline reminding them of the research, the financial incentive, and providing a further change of address notification form

The majority of data collection will take place in-home after making initial contact with individuals in-store and then arranging a home visit by telephone. There is further potential for drop-out between initial contact and baseline data collection. It will be the responsibility of NatCen fieldworkers to take account of this and the contract with NatCen will be to recruit and collect baseline data from a minimum of 38 individual participants per store.

# 26. DEBRIEFING

At the final contact with researchers, all participants in all components of the research will be asked if they would like to be informed of the study results when these become available. All those who indicate that they would, will be asked to provide their name and address (should this not already be on file). A written summary of the research aims and results will be sent to all those who indicate they would like this. This will occur as soon as possible after completion of all data collection.

# 27. STOPPING RULES

We do not propose any stopping rules or discontinuation criteria. Data will only be collected from individual cluster RCT participants at one follow up point and we will not be able to assess interim effects. We do not anticipate any serious negative impacts on individual cluster RCT participants of taking part in the research.

# 28. ANALYSES

# 28.1. Cluster RCT

#### 28.1.1. Coding of food diaries

Food diaries will be coded by trained coders and editors at the MRC Human Nutrition Research Unit, Cambridge (HNR). Food intakes will be entered into a modified version of HNR's dietary assessment system (Diet In Nutrients Out - DINO), an all-in-one dietary recording and analysis system. The food composition data in the FSA's NDNS nutrient databank will be used. Coders will assign food and portion codes from DINO to each item recorded in food diaries. Wrappers and labels collected by individual cluster RCT participants will also be used when coding. Within DINO, each food code is linked to appropriate portion size descriptors, mainly household measures, which are then linked to the correct weight for that food. Coding of portions,

described as small, medium or large, is based on the FSA's reference book.(20) In addition, where portion size is described as a weight, the weight can be entered directly in grams.

#### 28.1.2. Statistical analysis

For the primary outcome measure, the null hypothesis is that there is no difference in mean change in FFV intake from baseline to 12 months between individuals clustered around intervention and control stores. The alternative hypothesis is that the mean difference in the change between the two groups is not equal to zero. The null hypothesis will be tested using a multilevel model with random components for individuals and c-stores, and will be adjusted for baseline FFV intake and randomisation stratification variables. The multilevel model takes account of the clustering of individuals at the c-store level and adjusts standard errors appropriately. The result of this analysis will be presented as a 95% CI for the (adjusted) mean difference in the change in FFV intake between the two groups.

A multilevel modelling approach also allows variation in change in FFV intake to be partitioned in to store and individual levels. It permits the inclusion of characteristics of individuals and stores that are known (or hypothesised a priori) to be associated with the outcome of interest. Inclusion of such terms may reduce the estimate of the standard deviation of the effect and hence provide a more precise estimate of the effect of the intervention. The primary analysis will be by intention to treat. If necessary, a per-protocol analysis will also be performed, only including data from those stores that have complied with the intervention.

Exploratory analyses that incorporate interaction terms within and between levels and random coefficient terms at the store level will attempt to tease out "what works for whom, in what circumstances". However, formal hypothesis testing will be restricted to the primary outcome for which the study has been powered. All other hypothesis testing will be informal and interpreted as such.

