#### 18. INTERVENTIONS

#### 18.1. Intervention arm

The c-store C4L FFV intervention implemented in development stores involves an in-store 'toolkit', an in-store Fresh Food Champion, and regular support from the DH implementation team. As retailers make a substantial financial contribution to the cost of the intervention, it also involves the presence of a committed retailer. Although the main intervention components are consistent across stores, there will naturally be store-to-store variation in implementation, as expected in a pragmatic trial.

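### The supplementary per-protocol analysis keeps only complying stores; compliance is judged after randomisation and only in intervention stores, so it is not a randomised comparison

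*Protocol*

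**What the plan says.** Protocol section 28.1.2 states: "The primary analysis will be by intention to treat". It continues that, if necessary, "a per-protocol analysis will also be performed, only including data from those stores that have complied with the intervention". The same section confines formal testing to the primary outcome and adds: "All other hypothesis testing will be informal and interpreted as such".

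Four other sections decide what complying can mean here.

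- Section 20.3.1: fidelity and standard of implementation are assessed in intervention stores, with in-store observations at one and 12 months.
- Section 25.1.1: a store's drop-out from implementation is identified at the 12-month observation.
- Section 18.2: control stores follow usual practice and may change layout and stock as they wish. They have no access to the Department of Health's funding or support during the 12 months.
- Sections 21.1.1 and 22: allocation is one-to-one in pairs. "Within each pair one store will be randomised to the intervention arm of the study and one to the control arm".

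The protocol does not say whether the control partner of an excluded store stays in the per-protocol set.

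**The concern.** The criterion can remove intervention stores only, and it uses behaviour seen after allocation. Stores that implement may differ from those that do not in ways that also affect how their customers' diets change. Section 18.1 gives a reason to expect this. It says of the intervention that "it also involves the presence of a committed retailer", and section 18.1.1 leaves the retailer to find roughly £12,000 to £17,000 (£15,000–20,000 less about £3,000). Control stores with equally committed retailers cannot be picked out in the same way, because they are never asked to pay or deliver during follow-up.

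Non-compliance is foreseeable: section 18.1 expects implementation to vary between stores, and section 18.3 expects use of the toolkit to vary by store and over time. At stake is how a per-protocol estimate would be read beside the intention-to-treat result. Calling its test informal limits the claim of significance, but it does not remove bias from the estimate.

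**Working it through.** **Inputs** (section 14.1.1): target difference 40 g = 0.5 portions, so 80 g per portion; standard deviation of change 2.1 portions; intraclass correlation (ICC) 0.01, with 0.005 and 0.02 also considered; 80% power; two-sided 5%; 692 participants at follow-up in 14 + 14 stores. The number of non-complying stores is not in the document. I take 2, 4 and 7 of 14 as assumptions.

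**1. The plan's own figure.** Per arm, n = 2 × (1.960 + 0.842)² × (2.1/0.5)² ≈ 277 (278 from the t distribution). The design effect is 1 + (25 − 1) × 0.01 = 1.24. The total is 2 × 277 × 1.24 ≈ 687, or 2 × 278 × 1.24 ≈ 689. Working back from recruitment, 38 × 28 = 1064 and 1064 × 0.65 = 691.6. The stated 692 reproduces.

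**2. How far stores can differ.** Store-level standard deviation = 2.1 × √0.01 = 0.21 portions = 16.8 g/day.

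**3. Selection bias.** Suppose store effects are normal and compliance ranks stores perfectly by underlying change. The bias is then 0.21 times the mean standardised effect of the stores retained out of 14.

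| Stores dropped | Mean standardised effect of those kept | Bias, portions | Bias, g/day | Share of 40 g | Bias at correlation 0.5, g/day |
|---|---|---|---|---|---|
| 2 | 0.243 | 0.051 | 4.1 | 10% | 2.0 |
| 4 | 0.447 | 0.094 | 7.5 | 19% | 3.8 |
| 7 | 0.755 | 0.159 | 12.7 | 32% | 6.3 |

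At ICC 0.02 the perfect-selection figures are about 6, 11 and 18 g. At ICC 0.005 they are the 0.01 figures × √0.5: about 2.9, 5.3 and 9.0 g. Without normality, the ceiling at ICC 0.01 is 0.21 × √(dropped/kept): 0.21 × √(2/12) = 0.086, 0.21 × √(4/10) = 0.133 and 0.21 × √(7/7) = 0.21 portions, or about 7, 11 and 17 g.

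**4. Precision.** With 692/28 = 24.7 per store the design effect is 1.237.

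- Intention to treat, 14 v 14 stores: SE = 2.1 × √(1.237 × 2/346) = 0.178 portions.
- Per protocol, 10 v 14 stores: SE = 0.195.
- Whole pairs dropped, 10 v 10 stores: SE = 0.210.
- Complier-average estimate with 10 of 14 complying: the intention-to-treat estimate and its SE are both divided by 10/14, i.e. multiplied by 1.4. SE = 1.4 × 0.178 = 0.249.

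Power for 0.5 portions is 80% with all stores. It falls to 77%, 73% or 63% when 2, 4 or 7 intervention stores are dropped, and to 74%, 66% or 51% when whole pairs are dropped.

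**5. Why a strict compliance threshold is unsafe.** Suppose 10 stores implement fully with effect E and 4 implement half-way with effect E/2 (illustration only). The intention-to-treat effect is (10E + 4 × E/2)/14 = 0.857E. Counting only the 10 as compliers gives 1.4 × 0.857E = 1.2E, which is 20% too high. Dividing instead by the mean graded score, (10 × 1 + 4 × 0.5)/14 = 0.857, returns E. Counting any implementation as compliance divides by 14/14 and returns 0.857E, the average effect among implementing stores.

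**The case against.** The strongest reply is that one-sided, post-randomisation exclusion is a feature of almost every per-protocol analysis, and that this one is conditional, secondary to intention to treat and informally tested. The compliance threshold and the exact membership of the set may be in a statistical analysis plan that is not shown. This largely stands. It limits the point to a supporting analysis, and the missing definition alone would be no finding. What remains is the population the protocol does state, and a better estimate can be had from data already planned.

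A reader might infer more than the protocol supports:

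- **That the rule selects committed, better-resourced retailers and so favours the intervention.** This is plausible but is not stated. Section 11.1.1 requires every store in both arms to have expressed interest before randomisation. The model also adjusts for part of the store differences: it is a "multilevel model with random components for individuals and c-stores, and will be adjusted for baseline FFV intake and randomisation stratification variables", and section 21.1.1 stratifies on region, deprivation and store size.
- **That the analysis breaks the randomised pairs and is invalid for that reason.** Section 22 does say "We will employ simple randomisation within pairs of stores", but the protocol is silent on the partners of excluded stores, and the model names no pair term. If partners stay in, some balance is lost; the model itself is not invalidated.
- **That, read literally, no control stores remain.** The wording permits this, but a control store following usual practice would naturally be kept.
- **That the bias could exceed half the target effect.** Losing 8 of 14 stores with a gap of 0.5 portions between compliers and non-compliers would give (8/14) × 0.5 = 0.29 portions. That is above the ceiling of 0.21 × √(8/6) = 0.24 implied by the protocol's own variance figures.
- **That dropping both stores of a pair would cure it.** Pairs are drawn within region, deprivation and size strata and are not matched on commitment. The control partner's likely compliance stays unknown, and power falls further.

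**Conclusion.** The point holds as a modest weakness in a supplementary analysis. The per-protocol set is defined by a criterion that only intervention stores can fail and that is judged after randomisation, so its estimate is an observational comparison. At ICC 0.01 and standard deviation 2.1 portions, the bias under perfect selection is about 4 to 13 g/day for 2 to 7 stores dropped, and about half that at correlation 0.5. These figures rest on assumed numbers of non-complying stores, normal store effects, and an ICC that section 14.1.1 borrows from intake by postcode rather than change by store. The direction is likely to be favourable but is not established. The intention-to-treat result, the sample size and the main conclusion of the trial do not depend on it.

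**What to change.** Replace the per-protocol analysis with, or place beside it, a store-level complier-average estimate that keeps all 28 randomised stores. Use allocation as the instrument, implementation as scored at the 1- and 12-month observations, and the same covariates and store random effect as the primary model. Set implementation to zero in control stores, which have no access to the programme's funding or support under section 18.2.

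Fix the compliance definition before outcomes are linked to allocation. Use the graded implementation score, or count any implementation as compliance; a strict binary threshold would inflate the estimate if partly implementing stores had some effect. The graded version assumes that the effect is proportional to the score, and this should be stated. Replace the open condition for running the analysis with a fixed one. If a per-protocol estimate is kept, state how control stores and the partners of excluded stores are handled, and label it non-randomised and descriptive.

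The cost is wording and one model, with no new data. The estimate relies on the exclusion restriction, that allocation acts only through implementation. Its interval is wider: SE about 0.25 against 0.18 portions for intention to treat if 10 of 14 stores comply. With the compliance share treated as fixed, the estimate and its SE scale together, so it cannot turn a null intention-to-treat result into a positive one.
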